9. PRIMARY SAFETY ANALYSES

All participants enrolled and administered a study product will be assessed for safety.

9.1 Primary Safety Analyses

The primary safety endpoint is defined as follows:

Grade 2 or higher related adverse events (AEs) as defined by the Division of AIDS Table for Grading the Severity of Adult and Pediatric Adverse Events, Corrected Version 2.1, July 2017, and/or Addenda 1, 2 and 3 (Female Genital [Dated November 2007], Male Genital [Dated November 2007] and Rectal [Clarification Dated May 2012] Grading Tables for Use in Microbicide Studies)

The number and the percentage of participants experiencing each safety endpoint will be tabulated by study product. This table will display a summary for any primary safety endpoint and for each individual safety endpoint. Each participant will contribute once in each category (i.e., only for highest severity AE for each participant) for the calculation of event rates for each study product. Exact binomial confidence intervals (Clopper-Pearson) will be calculated for each safety endpoint, even if no events occur for an endpoint for a particular study product.

9.2 Adverse Events

Summaries of adverse events will include a cumulative listing of adverse events, a table displaying the total number of adverse events by severity grade and relationship to study product, a table of the incidence of adverse events by MedDRA organ system class/preferred term and severity, and a table of incidence of adverse events by MedDRA organ system class/preferred term and relationship to study product. Tables above will be displayed by site and displayed by study product. The listing will include the study product used period when the AE occurred.

9.3 Other Safety Measures

Additional safety summaries include:

The number and percentage of participants with a positive result for hCG for pregnancy and HIV will be displayed in a table overall and by site if applicable. A listing of participants with positive results of STI testing (syphilis, trichomonas, gonorrhea, chlamydia) after first study product use will be presented if applicable.

A listing of participants with abnormal findings on rectal exam after first study product used will be presented.

A listing of all concomitant medications will be presented.

10. Exploratory Analysis

In addition to the analyses described above, the following analyses will be conducted to compare and estimate the relative acceptability/tolerance, adherence and safety between the three study products. These analyses will also allow to assess potential effects of the order of product use on each of the endpoints.

A logistic mixed effects regression model will be used to estimate the relative odds (odds ratios) of high acceptability between the different study products. A similar logistic mixed effects regression model will be used to estimate the relative odds (odds ratio) of full per-protocol and per-sex-act adherence between the different study products. To account for the cross-over design of the study, a random intercept at the participant level will be included in the models. Estimates of the odds-ratios, along with 95% confidence intervals and associated p-values will be reported. If feasible, testing for effects of the order of product use will be done by including interaction terms between study product and randomized sequence in the model.

A logistic mixed effects regression model will be used to estimate the relative odds (odds ratio) of having a primary safety endpoint, as defined in section 9.1, between the different study products. A Poisson mixed effects regression model will be used to compare the incidence (expected counts) of AEs per study period between the study products. If feasible, interaction terms between study product and randomized sequence will be included in the model to test the effect of order of product use on the safety endpoints.

11. References

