B0. The following questions refer to your use of the study provided rectal [**study product: douche/enema, insert or suppository**] over the past 4 weeks. You were asked to insert the study provided rectal [**study product**] in your rectum at least once a week during the past 4 weeks. However, for different reasons, people might have encountered difficulties using the [**study product**]. Thinking about your experience during these past four weeks, in how many of the weeks did you miss a rectal [**study product**] application?

- 0 weeks
- 1 week
- 2 weeks
- 3 weeks
- 4 weeks

Responses to question B0 will be tabulated by study product, study product and sequence and study product and site, along with the number and proportion of participants fully adherent (those

who reported 0 weeks missing application), with 95% confidence intervals (Clopper- Pearson). If needed, additional categories of invalid/missing responses will be included.

- 2. Adherence per sex-act:** Proportion of times when participants reported having used the study-provided rectal douche/enema, insert or suppository before receptive anal sex. For participants who reported at least 1 anal sex act in the previous 4 weeks, this proportion will be obtained by dividing the number reported in Question B2 over the number reported in Question B1 of the CASI:

B1. How many times did a partner put a penis in your rectum during the past 4 weeks?

B2. Of those [] times, how many times did you use the study-provided rectal **[study product: douche/enema, insert or suppository]** BEFORE receptive anal sex? (If you did not use the douche prior to anal sex, please enter '0'.)

Responses to Questions B1 and B2 will be cross tabulated, by study product and by study product and site. If needed, additional categories of invalid/missing responses will be included. Summary statistics (mean and SD, median and IQR) of participants' per sex-act adherence, as defined above, will be displayed by study product and by study product and site.

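### The SAP defines per-sex-act adherence as a proportion but appears to compare products on full versus not full, an undefined outcome that loses information and depends on the number of acts

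*SAP*

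**What the plan says.** SAP section 8 (Primary Endpoints) has two adherence endpoints. The weekly one, from CASI item B0, counts a participant as fully adherent if they are among those "who reported 0 weeks missing application". The per-sex-act one is a "Proportion of times when participants reported having used the study-provided rectal douche/enema, insert or suppository before receptive anal sex", and "this proportion will be obtained by dividing the number reported in Question B2 over the number reported in Question B1 of the CASI". It applies to a restricted group: "For participants who reported at least 1 anal sex act in the previous 4 weeks". It is summarised by mean, SD, median and IQR for each product, and "Responses to Questions B1 and B2 will be cross tabulated, by study product and by study product and site".

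SAP section 10 (Exploratory Analysis) compares products with a logistic mixed model to "estimate the relative odds (odds ratio) of full per-protocol and per-sex-act adherence between the different study products". For the crossover, "a random intercept at the participant level will be included in the models". The other terms named are product and, if feasible, product-by-sequence interactions. The number of acts appears neither as a covariate nor as a denominator. Odds ratios, 95% confidence intervals and p-values will be reported.

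In the phrase "full per-protocol and per-sex-act adherence", the adjective *full* naturally governs both adherence terms, yet the SAP defines it only for B0. Section 10 does not say whether the per-act response is one yes/no value per period or B2 events out of B1 trials.

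**The concern.** On the natural reading, section 10 replaces the section 8 endpoint with an indicator of B2 = B1. Two consequences follow.

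The first needs no behavioural assumption. A period with 7 of 8 acts covered counts the same as one with 0 of 8, so the product comparison is less precise than the CASI data allow.

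The second is conditional. When per-act use is below 100%, the chance of covering every act falls as acts increase. B1 is recorded after randomisation in an open-label trial, so a product could alter how often the same person has receptive anal intercourse (RAI). Protocol section 2.3.2 reports drawbacks that potential users foresaw for a douche, including lack of time before sex and the inconvenience of carrying it. If acts fell in one product's periods, that product would show better full adherence with no difference in use per act.

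At stake is the only inferential comparison of per-act adherence between products. The section 8 summaries of this endpoint carry no interval or test.

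**Working it through.** **1. The plan's own figures.** SAP Table 2 uses n = 200 and two-sided alpha 0.05. An observed 80% gives an exact interval of 73.8–85.3% (stated 74, 85). The smallest count whose lower limit exceeds 70% is 153, and for 75% it is 163. The power results are:
- true rate 80%: P(X ≥ 153) = 90.6% (stated 90%) and P(X ≥ 163) = 33.5% (stated 35%);
- true rate 85%: P(X ≥ 163) = 92.8% (stated 93%).

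These reproduce to within 2 points. They concern a single adherence rate. Neither document gives a figure for the per-act product comparison, nor an expected act count or per-act use. Those inputs are assumptions below.

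**2. Dependence of *full* on act count.** With constant per-act use p and k acts, P(full) = p^k.

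| p | k = 1 | k = 4 | k = 8 | k = 12 |
|---|---|---|---|---|
| 0.80 | 0.80 | 0.41 | 0.17 | 0.07 |
| 0.90 | 0.90 | 0.66 | 0.43 | 0.28 |
| 0.95 | 0.95 | 0.81 | 0.66 | 0.54 |

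At p = 0.90, the odds of full adherence are 0.656/0.344 = 1.91 with 4 acts and 0.430/0.570 = 0.76 with 8. The odds ratio is 2.52 with per-act use unchanged. The same contrast gives 3.44 at p = 0.80 and 2.23 at p = 0.95.

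**3. The SAP's type of model.** I simulated a three-product crossover: 200 participants, 200 runs, gamma-Poisson acts (shape 1.5, mean 6), typical per-act use 0.90, participant logit SD 1, and no true product effect on per-act use. A random-intercept logistic model was fitted to full/not-full, then to B2 out of B1.

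| Acts on third product, relative to the others | Full/not-full: OR, rejection | B2 of B1: OR, rejection |
|---|---|---|
| 100% | 0.98, 6.5% | 1.02, 3.0% |
| 75% | 1.40, 26% | 1.01, 4.5% |
| 50% | 2.14, 82.5% | 1.00, 4.5% |

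The Monte Carlo standard error near 5% is √(0.05 × 0.95/200) = 1.5 points. With mean 4 acts and equal frequency, full/not-full gives OR 0.99 and 3.5% rejection. The first row matters: act frequency varies widely between people there, yet no bias appears.

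**4. Size over a range.** Simulated pairs of periods (n = 180, logit SD 1) compared a mid-p McNemar test on full/not-full with an act-level difference in ratios using participant-clustered variance. Both tests are stand-ins for the mixed models.

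*Power*, mean 5 acts in both periods, per-act use 90% v 85%:

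| Within-person overdispersion SD (logit) | Full/not-full | Act level |
|---|---|---|
| 0 | 50% | 87% |
| 0.7 | 45% | 70% |
| 1.0 | 36% | 53% |

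*False rejection*, equal per-act use of 90%:

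| Mean acts | Full/not-full | Act level |
|---|---|---|
| 5 v 5 | about 5% | about 5% |
| 6 v 5 | 11–15% | about 5% |
| 6 v 4 | 31–48% | about 5% |

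The ranges cover different assumptions about overdispersion and the spread of act counts. Smaller shifts do less: full/not-full rejects in about 8% of trials at 5.25 v 4.75 acts and 13% at 5.5 v 4.5.

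**5. Would a lower cut-off help?** The sample-size text speaks of 90% of expected doses. With 9 acts, 8/9 = 0.889 fails a 90% rule, so at 9 or fewer acts it still requires every act.

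**The case against.** The strongest reply is that the SAP does not state the collapse. Full adherence is defined only for B0, and a logistic mixed model can take B2 events out of B1 trials. That stands: what can be documented is an undefined response, with full/not-full as its likely meaning.

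A reader might also infer that participants with many acts fail by arithmetic alone, or that differences in sexual frequency between people will pass for differences in adherence. The documents support neither inference. Someone who uses product before every act is fully adherent at any count. Each participant is also scheduled to use all three products, in six balanced sequences with a participant random intercept, and the equal-frequency simulations show no bias. Bias needs act frequency to differ by product within the same person. No evidence of that is given, and Protocol section 5.2 (inclusion criterion 7) asks participants to expect to keep up a minimum frequency of RAI. That criterion sets a floor of three acts in three months and no ceiling, so it does not exclude a shift.

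The setting limits the harm. The analysis is exploratory, Protocol section 10.7.1 plans no product comparison in the primary acceptability and adherence analysis, and the section 8 cross tabulation would reveal a shift in acts by product. It would not correct the section 10 odds ratio or recover its lost precision.

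Finally, covering every act is a legitimate estimand for an on-demand product, which is a reason to keep it as a summary. An act-level model is not free of dependence either. Protocol section 6.2 recommends at most one dose in 24 hours, so acts close together are not independent opportunities for use. That argues for an overdispersion term.

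**Conclusion.** The point holds in a limited form. Section 10 leaves the per-act response undefined, and its natural reading discards most of what B1 and B2 record. The information loss applies whenever some participants use product before some but not all acts. Under the assumed inputs, power falls from 53–87% to 36–50%.

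Bias is conditional on a within-participant product effect on act frequency, which is plausible but not shown. If acts differed by 6 v 5, false rejection would be roughly two to three times the nominal 5%; at 6 v 4 it would be about 31–48%. It would be wrong to conclude that the planned odds ratio is biased as things stand.

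All these sizes rest on assumed act counts, per-act use, between-person spread and n = 180 (the SAP's sample-size text assumes 200 evaluable). The directions are firmer than the figures. The primary descriptive results are unaffected. This is a worthwhile improvement to an exploratory analysis.

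**What to change.** In SAP section 10, state the per-sex-act response explicitly and model B2 successes out of B1 acts in a binomial mixed model. Include fixed effects for product and period, a participant random intercept, and a participant-by-period random effect (or a beta-binomial distribution) for overdispersion. Report per-act odds ratios with 95% confidence intervals.

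Alongside the model, report the distribution of B1 and the number of participants with zero acts by product, so that any product effect on frequency, or on who enters the endpoint, is visible. Define full per-sex-act adherence as B2 = B1 with B1 at least 1, and keep it as a descriptive summary by product.

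The cost is SAP wording and a modest change in programming. The CASI items are the same, and no new data, visits or participants are needed.

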## **10.7 Data Analyses**

### **10.7.1 Primary Analyses on Acceptability/Tolerability and Adherence Measures**

All primary analyses will be based on data from the participants with data in all three periods of study (participants who complete each period of the study). Baseline values between these participants and those participants lost to follow-up will be described and used to interpret the generalizability of the results. Additionally, secondary analyses will analyze endpoints among all participants. The adherence and acceptability/tolerability endpoints (defined in Section 10.3.1) will be reported with 95% CI. The purpose of this protocol is not to compare the placebo products; therefore, we do not plan on doing comparisons between products in the primary analysis. Logistic regression models will be used to assess the order of product use (period effect) on acceptability/tolerance and adherence.

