### **10.7.2 Primary Analysis on Safety Measures**

All visits in which a participant has been exposed to the study product will be included in the primary analyses of safety. Secondary analyses including the washout period may also be performed. The number and the percentages of participants experiencing each safety endpoint (see Section 10.2) will be tabulated by study arm. Each participant will contribute once in each category (i.e., only for highest severity AE for each participant) for the calculation of event rates. Exact binomial confidence intervals will be calculated for each safety endpoint for each arm and Fisher's Exact test will be used to test for differences in event rates between the arms. Logistic and Poisson regression models will be used to assess the order of product use (period effect) on safety endpoints.

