8. PRIMARY ENDPOINTS

The acceptability, tolerability and adherence primary endpoints will be evaluated on the per-protocol subset of participants, i.e. participants who received all three study products and completed the corresponding PUEV, and thus provide relevant data from all three periods of study. Assessment of these endpoints will be based on responses from the participants to the computer assisted self-interviews (CASI) at the three PUEVs (Visits 3, 5 and 7). To aid in the interpretation of the resulting analyses, baseline characteristics of the per-protocol subset of participants including, but not limited to, study site, sequence, sex/gender, and age will be described and compared to those of participants who were lost to follow-up.

Acceptability and Tolerability

The acceptability and tolerability endpoint will be based on question H1 of the CASI:

“Think about the positive and negative experiences you have had using the rectal Insert during the past 4 week period. If this rectal insert was available and it provided some protection against HIV, how likely would you be to use it before receptive anal sex?”.

Responses to this question for each product were captured from visual Likert scale from 1 (very unlikely) to 10 (very likely). Participants’ responses corresponding to the three product use periods will be displayed in tables by study product, by study product and site and by study product and randomization sequence.

To compare acceptability and tolerability between study products, the endpoint will be operationalized as binary, with scores 1 to 6 grouped as “low acceptability” and scores 7 – 10 as “high acceptability”. Number and percentage of participants giving a “high acceptability” score will be display in tables by study product, with exact binomial 95% confidence intervals (Clopper-Pearson method).

Adherence

Two endpoints related to adherence will be assessed: adherence to use per-protocol and adherence to use per-anal-sex-act. These are defined as follows:

1. **Adherence to use per-protocol:** Number and proportion of participants who reported not having missed a rectal [enema/douche, insert or suppository] application in the previous 4 weeks, according to the participants’ response to question B0 of the CASI:

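### The protocol promises a model-based assessment of period effects, but no SAP Section 10 model has a period term; order is tested only through a conditional product-by-sequence interaction

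*SAP*

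**What the plan says.** Protocol 10.7.1 states: "Logistic regression models will be used to assess the order of product use (period effect) on acceptability/tolerance and adherence". Protocol 10.7.2 makes the matching commitment for safety: "Logistic and Poisson regression models will be used to assess the order of product use (period effect) on safety endpoints". Neither sentence carries a condition, and both gloss order of use as a period effect.

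SAP Section 10 (Exploratory Analysis) sets a wider aim: "These analyses will also allow to assess potential effects of the order of product use on each of the endpoints". Its models contain study product and a participant random intercept. For acceptability and adherence, subject to feasibility, "testing for effects of the order of product use will be done by including interaction terms between study product and randomized sequence". For safety, under the same condition, "interaction terms between study product and randomized sequence will be included in the model to test the effect of order of product use". The word period appears in the description of one of these models, "A Poisson mixed effects regression model will be used to compare the incidence (expected counts) of AEs per study period between the study products", but there it is the unit over which events are counted, not a covariate. The SAP does not say whether sequence main effects are fitted alongside the interaction.

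Some descriptive material bears on period. SAP Section 8 displays acceptability responses "by study product and site and by study product and randomization sequence" and tabulates the missed-weeks adherence question (B0) by product and sequence. For adverse events, SAP 9.2 adds: "The listing will include the study product used period when the AE occurred".

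**The concern.** The two current documents do not plan the same thing. The protocol names a specific effect and promises to model it. The SAP replaces it with a broader test that may not be run.

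In this design a sequence and a product together fix the period, so product by sequence does contain the period effect. It also contains carryover and every other way in which order could matter. Two things follow if the interaction is judged as a whole. Its power for a simple shift across periods is diluted, so a non-significant result is weak evidence against the effect named in the protocol. A significant result does not say which order effect produced it. No period test, estimate or confidence interval is planned anywhere.

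**Working it through.** **Inputs.** Six sequences, three periods and three products (SAP Table 1); equal allocation (SAP 2.3); 200 evaluable of 210 (SAP 2.5), that is 200/6 ≈ 33 to 210/6 = 35 participants per sequence; safety event rates from SAP Table 3. The documents give no alpha for the order test and no period effect size. I assume alpha 0.05 and compare tests at equal noncentrality.

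**The plan's own figures.** No power or degrees of freedom is stated for any order test. The zero-event column of SAP Table 3 reproduces from (1−r)^200: 36.7%, 13.4% and 1.8% at r = 0.5%, 1% and 2%, against the stated 37%, 13% and 2%.

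**Degrees of freedom.** Rank of the design matrix over the 18 product-sequence cells:

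| Model | Rank |
|---|---|
| product + sequence | 8 |
| + period | 10 |
| + period + previous product | 12 |
| + product × sequence | 18 (saturated) |

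The interaction adds 18 − 8 = 10 df: period 10 − 8 = 2, first-order carryover 12 − 10 = 2, other patterns 18 − 12 = 6. Without sequence main effects, product alone has rank 3 and the interaction adds 18 − 3 = 15.

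**Power for an additive period effect** (noncentral chi-square):

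| Noncentrality | Period, 2 df | Interaction, 10 df | Interaction, 15 df |
|---|---|---|---|
| 9.63 | 80% | 52% | 44% |
| 12.65 | 90% | 67% | 58% |

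The 10-df test needs noncentrality 16.24 for 80% power, and 16.24/9.63 = 1.69 times the information. A simulation of binary outcomes (n = 200, random-intercept SD 1, 1,500 runs per scenario) agrees. With period rates of about 79%, 73% and 66%, power is 85% against 59%; with 79%, 75% and 70%, 54% against 33%; with 79%, 76% and 73%, 28% against 16%.

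**The reverse comparison.** Set the 10-df test at 80% power (noncentrality 16.24) and project each pattern on the design, with equal cells, sequence main effects fitted and a large-sample approximation:

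| Pattern | Period test | Previous-product test, given period |
|---|---|---|
| Linear period effect | 96% | 5% |
| Carryover after one product | 35% | 91% |
| Opposite carryovers after two products | 5% | 96% |
| One product differs only when used last | 72% | 9% |
| One product rises over periods while another falls | 5% | 5% |

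**Effect on product comparisons.** Each product occurs in each period in 2 of the 6 sequences. Product and period columns are orthogonal (maximum cross-product 0).

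**Sparsity for the primary safety endpoint.** Expected empty cells are 18 × (1−r)^n with n = 33 to 35. The chance that at least one of the three periods has no event, with n = 200, is 1 − (1 − (1−r)^200)^3.

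| Event rate | Empty cells of 18 | At least one event-free period |
|---|---|---|
| 0.5% | 15.3 to 15.1 | 75% |
| 1% | 12.9 to 12.7 | 35% |
| 2% | 9.2 to 8.9 | 5% |

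At 5%, the top rate in SAP Table 3, about 3 cells are expected to be empty (18 × 0.95^35 = 3.0). The Poisson model of all adverse events may be less sparse, but the documents give no rate for those.

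**The case against.** The best defence is that the SAP does plan a model-based look at order, and that period lies wholly inside it: adding period to the interaction model leaves the rank at 18. SAP Section 10 asks about order in general, which can mean that a product's rating depends on when it was used. Where one product rises over periods while another falls, the interaction is the right test and both 2-df tests have no power beyond alpha. That stands, and it is why the interaction should be kept. It does not supply the period assessment the protocol names, since no period contrast is specified.

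The size of the power gap also depends on assumptions. The 80% anchor is arbitrary, and for a modest shift (79% to 73%) both tests are weak. If period and previous product are each tested at 0.025 to allow for two tests, 80% becomes 71% and 91% becomes 85%. Both remain above the omnibus at the same effects (52% and 80% respectively). The 15-df figures apply only if sequence main effects are omitted, which the SAP leaves open.

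The by-sequence tables and the adverse event listing let a reader see period descriptively. The protocol promised regression models. Finally, the feasibility condition is a sensible guard where safety events are sparse, and a period term can fail there too. I accept this for safety. It is a weaker reason for making the acceptability and adherence assessment conditional.

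**Conclusion.** The concern holds, at low to moderate priority. The SAP turns an unconditional commitment to assess period into a conditional test of a broader hypothesis. For an additive period effect the power falls from 80% to 52%, or from 90% to 67%, on 10 df, and the result does not identify period. A period term plus a previous-product term covers additive period and first-order carryover better than the omnibus test; the omnibus test is better only for other patterns.

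This is a loss of power and interpretability in an exploratory analysis, not a bias. The primary by-product estimates and the product odds ratios are not materially affected while the design stays close to balanced. For the primary safety endpoint at 1% to 2% event rates, most individual interaction odds ratios will not be estimable and any omnibus test will be unreliable, whether or not period is added.

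The power figures assume alpha 0.05, equal cells and large-sample approximations.

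**What to change.** In each SAP Section 10 model, fitted without the product-by-sequence interaction, add period (1, 2, 3) as a fixed effect next to product. Report its 2-df test and estimates as the period assessment promised in Protocol 10.7. As separate secondary checks, test a 2-df previous-product term for carryover and, where estimable, product by sequence for other order effects. State whether sequence main effects are fitted.

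For the primary safety endpoint, show event counts by period with exact confidence intervals, and use a penalised or exact method if a model is fitted.

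The cost is SAP wording, two more parameters per model (a further two where previous product is tested) and a little more analysis work, including the safety tables and any penalised or exact fit. No new data are needed.
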